## **8.1. Efficacy Assessments**

Not applicable.

## **8.2. Safety Assessments**

Planned time points for all safety assessments are provided in the [SoA](#). Unscheduled clinical laboratory measurements may be obtained at any time during the study to assess any perceived safety issues.

### **8.2.1. Physical Examinations**

[figure not shown]
A complete physical examination will include, at a minimum, head, ears, eyes, nose, mouth, skin, heart and lung examinations, lymph nodes, and gastrointestinal, musculoskeletal, and neurological systems.

A brief physical examination will include, at a minimum, assessments of general appearance, the respiratory and cardiovascular systems, and participant-reported symptoms.

Physical examinations may be conducted by a physician, trained physician's assistant, or nurse practitioner as acceptable according to local regulation.

Height and weight will also be measured and recorded as per the [SoA](#). For measuring weight, a scale with appropriate range and resolution is used and must be placed on a stable, flat surface. Participants must remove shoes, bulky layers of clothing, and jackets so that only light clothing remains. They must also remove the contents of their pockets and remain still during measurement of weight.

PFIZER CONFIDENTIAL

Physical examination findings collected during the study will be considered source data and will not be required to be reported, unless otherwise noted. Any untoward physical examination findings that are identified during the active collection period and meet the definition of an AE or SAE ([Appendix 3](#)) must be reported according to the processes in [Sections 8.3.1 to 8.3.3](#).

### **8.2.2. Injection Site Assessment**

Injection site reactions will be assessed according to the [SoA](#). Additional assessments may be conducted at investigator discretion and/or until any symptoms resolve. Injection site reactions may include but are not limited to: erythema, induration, ecchymosis, pain, and pruritus. The size and severity of injection site reactions will be assessed and documented. If deemed appropriate by the investigator, a consultation with a dermatologist may be performed. Documentation of a reaction may include items such as investigator notes, photographs, dermatologist report, and/or clinic notes.

### **8.2.3. Vital Signs**

Supine BP will be measured with the participant's arm supported at the level of the heart, and recorded to the nearest mm Hg after approximately 5 minutes of rest. The same arm (preferably the dominant arm) will be used throughout the study. Participants should be instructed not to speak during measurements.

When triplicate BP and PR are required (on Day 1), they will be obtained approximately 2 to 4 minutes apart; the average of the triplicate BP and PR measurements collected prior to dosing on Day 1 will serve as each participant's baseline value.

The same properly sized and calibrated BP cuff will be used to measure BP each time. The use of an automated device for measuring BP and pulse rate is acceptable; however, when done manually, pulse rate will be measured in the brachial/radial artery for at least 30 seconds. When the timing of these measurements coincides with a blood collection, BP and pulse rate should be obtained prior to the nominal time of the blood collection.

Additional collection times of BP and pulse rate will be permitted, as necessary, to ensure appropriate collection of safety data.

### **8.2.4. Electrocardiograms**

Standard 12-lead ECGs utilizing limb leads (with a 10 second rhythm strip) should be collected at times specified in the [SoA](#) section of this protocol using an ECG machine that automatically calculates the heart rate and measures PR, QT, and QTcF intervals and QRS complex. The timing of the PK samples should drive the timing of the ECGs. Note that ECGs do not need to be recorded at every time a PK sample is collected, but whenever an ECG is recorded, a PK sample should be collected at approximately the same time (preferably immediately after). Alternative lead placement methodology using torso leads (eg, Mason-Likar) should not be used given the potential risk of discrepancies with ECGs

PFIZER CONFIDENTIAL

acquired using standard limb lead placement. All scheduled ECGs should be performed after the participant has rested quietly for at least 5 minutes in a supine position.

TriPLICATE standard 12-lead ECGs will be obtained approximately within 5 minutes. The average of the triplicate ECG measurements collected prior to dosing on Day 1 will serve as each participant's baseline value.

To ensure safety of the participants, a qualified individual at the investigator site will make comparisons to baseline measurements. Additional ECG monitoring will occur if a) the mean value from the triplicate measurements for any postdose QTcF interval is increased by  $\geq 60$  ms from the baseline and is  $>450$  ms; or b) an absolute QT value is  $\geq 500$  ms for any scheduled ECG. If either of these conditions occurs, then a single ECG measurement must be repeated at least hourly until QTcF values from 2 successive ECGs fall below the threshold value that triggered the repeat measurement.

If a) a postdose QTcF interval remains  $\geq 60$  msec from the baseline and is  $>450$  msec; or b) an absolute QT value is  $\geq 500$  msec for any scheduled ECG for greater than 4 hours (or sooner, at the discretion of the investigator); or c) QTcF intervals get progressively longer, the participant should undergo continuous ECG monitoring. A cardiologist should be consulted if QTcF intervals do not return to less than the criteria listed above after 8 hours of monitoring (or sooner, at the discretion of the investigator).

In some cases, it may be appropriate to repeat abnormal ECGs to rule out improper lead placement as contributing to the ECG abnormality. It is important that leads be placed in the same positions each time in order to achieve precise ECG recordings. If a machine-read QTcF value is prolonged, as defined above, repeat measurements may not be necessary if a qualified medical provider's interpretation determines that the QTcF values are in the acceptable range.

ECG values of potential clinical concern are listed in [Appendix 6](#).

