| Assessment of eligibility,
medical/medication history c           | X         | X                                     |                       |       |       |       |       |        |               |           |           |           |           |           |            |   |
| Physical exam and weight (plus height
at Screening, only) d       | X         | X                                     |                       |       |       |       |       |        | X             | X         | X         | X         | X         | X         | X          | X |
| Review alcohol/caffeine/tobacco, as
applicable                               | X         | X                                     |                       |       |       |       |       |        | X             | X         | X         | X         | X         | X         | X          | X |
| Review prior or concomitant
treatments, as applicable                        | X         | X                                     | →                     | →     | →     | →     | →     | →      | →             | →         | →         | →         | →         | →         | →          | X |
| Demography  | X         |                                       |                       |       |       |       |       |        |               |           |           |           |           |           |            |   |
| Review contraception use  | X         | X                                     |                       |       |       |       |       |        | X             | X         | X         | X         | X         | X         | X          | X |
| Serious and non-serious AEs
monitoring                                       | X         | X                                     | →                     | →     | →     | →     | →     | →      | →             | →         | →         | →         | →         | →         | →          | X |
| Injection site assessment e  |           |                                       | X                     | →     | X     |       |       |        |               |           |           |           |           |           |            |   |
| Supine 12-lead ECG (triplicate)   | X         |                                       | X f        |       | X     | X     |       | X      | X             |           |           | X         | X         |           |            | X |

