**Diagnostic Assessments:**

10. A positive urine drug test.
11. Screening supine BP  $\geq 140$  mm Hg (systolic) or  $\geq 90$  mm Hg (diastolic), following at least 5 minutes of supine rest. If BP is  $\geq 140$  mm Hg (systolic) or  $\geq 90$  mm Hg (diastolic), the BP should be repeated 2 more times and the average of the 3 BP values should be used to determine the participant's eligibility.
12. Screening 12-lead ECG that demonstrates clinically relevant abnormalities that may affect participant safety or interpretation of study results (eg, baseline QTcF interval  $>450$  msec, or QRS interval  $>120$  msec). If the baseline uncorrected QT interval is

PFIZER CONFIDENTIAL

>450 msec, this interval should be rate-corrected using the Fridericia method and the resulting QTcF should be used for decision making and reporting. If QTcF exceeds 450 msec, or QRS exceeds 120 msec, the ECG should be repeated 2 more times and the average of the 3 QTcF or QRS values should be used to determine the participant's eligibility. Computer-interpreted ECGs should be overread by a physician experienced in reading ECGs before excluding a participant.

13. Participants with **ANY** of the following abnormalities in clinical laboratory tests at screening, as assessed by the study-specific laboratory and confirmed by a single repeat test, if deemed necessary:
  - AST **or** ALT level  $\geq 1.5 \times$  ULN;
  - Total bilirubin level  $\geq 1.5 \times$  ULN; participants with a history of Gilbert's syndrome may have direct bilirubin measured and would be eligible for this study provided the direct bilirubin level is  $\leq$  ULN.
14. COVID-19 positive.

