#### 9.3.2.1. Electrocardiogram Analyses

Changes from baseline for the ECG parameters QT interval, heart rate, QTcF interval, PR interval, and QRS interval will be summarized by cohort and time.

The number (%) of participants with maximum postdose QTcF values and maximum increases from baseline in the following categories will be tabulated by cohort:

| Safety QTcF Assessment |             |                 |               |
|------------------------|-------------|-----------------|---------------|
| Degree of Prolongation | Mild (msec) | Moderate (msec) | Severe (msec) |
| Absolute value         | >450-480    | >480-500        | >500          |
| Increase from baseline |             | 30-60           | >60           |

If more than 1 ECG is collected at a nominal time after dose administration (for example, triplicate ECGs), the mean of the replicate measurements will be used to represent a single

PFIZER CONFIDENTIAL

observation at that time point. If any of the 3 individual ECG tracings has a QTc value >500 msec, but the mean of the triplicates is not >500 msec, the data from the participant's individual tracing will be described in a safety section of the CSR in order to place the >500-msec value in appropriate clinical context. However, values from individual tracings within triplicate measurements that are >500 msec will not be included in the categorical analysis unless the average from the triplicate measurements is also >500 msec. Changes from baseline will be defined as the change between the postdose QTc value and the average of the predose triplicate values on Day 1.

In addition, the number of participants with uncorrected QT values >500 msec will be summarized.

CCI

[figure not shown]

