#### **ECG Findings That Qualify as SAEs**

- Change in pattern suggestive of new myocardial infarction.
- Sustained ventricular tachyarrhythmias (>30 seconds' duration).
- Second- or third-degree AV block requiring pacemaker placement.
- Asystolic pauses requiring pacemaker placement.
- Atrial flutter or fibrillation with rapid ventricular response requiring cardioversion.
- Ventricular fibrillation/flutter.
- At the discretion of the investigator, any arrhythmia classified as an adverse experience.

[figure not shown]
The enumerated list of major events of potential clinical concern are recommended as “alerts” or notifications from the core ECG laboratory to the investigator and Pfizer study team, and not to be considered as all inclusive of what to be reported as AEs/SAEs.

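### Protocol 8.2.4 starts repeat ECGs on absolute QT of 500 ms or more but ends them on QTcF, so at slow heart rates the series can stop with QT still at or above 500 ms

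*Protocol*

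**What the plan says.** Protocol 8.2.4 sets two triggers for additional ECG monitoring after dosing. Trigger (a) is a triplicate-mean QTcF at least 60 ms above baseline and also above 450 ms. Trigger (b) is worded "or b) an absolute QT value is" 500 ms or more on a scheduled ECG. After either, single ECGs are required at least hourly "until QTcF values from 2 successive ECGs fall below the threshold value that triggered the repeat measurement".

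The next paragraph of 8.2.4 moves the participant to continuous monitoring in any of three cases: the QTcF condition persists, absolute QT is at or above 500 ms for more than 4 hours, or QTcF keeps lengthening. Escalation beyond that is on QTcF: "A cardiologist should be consulted if QTcF intervals do not return to less than the criteria listed above after 8 hours of monitoring". The over-read provision is also about QTcF: "If a machine-read QTcF value is prolonged, as defined above, repeat measurements may not be necessary" if a qualified reader finds the QTcF acceptable.

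Three other places bear on the point:

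- Section 5.2, exclusion criterion 12, rate-corrects a long screening QT and says the "resulting QTcF should be used for decision making and reporting".
- Section 9.3.2.1 tabulates QTcF categories and adds that "the number of participants with uncorrected QT values >500 msec will be summarized".
- Appendix 6 lists QTcF above 480 ms, or a rise of at least 60 ms, as a possible AE, and QTcF above 500 ms as a possible SAE. It lists no uncorrected QT value.

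**The concern.** The rule that opens trigger (b) and the rule that closes it use different intervals. Section 8.2.4 lists QT and QTcF as separate machine outputs, so the two terms cannot simply be taken as the same thing.

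**Gap 1.** Below 60 bpm QTcF is smaller than QT. A participant whose QT alone reached 500 ms may already have a QTcF under 500 ms. The first two repeats then satisfy the release rule although nothing has changed.

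**Gap 2.** Section 8.2.4 has no absolute QTcF trigger. Above about 60 bpm, a QTcF over 500 ms can meet neither (a) nor (b) if baseline was already high.

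This is a mandatory participant-safety rule, so it should work when followed exactly. What is at stake is the follow-up of an individual with a prolonged interval, not the trial's PK results.

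**Working it through.** The plan gives no figure to reproduce here, so the check follows the rules through with the Fridericia formula, which the protocol uses.

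**Inputs.** The thresholds are those of 8.2.4: QT 500 ms, a QTcF rise of 60 ms, and QTcF 450 ms. The 480 and 500 ms flags come from Appendix 6, and the 450 ms screening limit from exclusion criterion 12. Heart rates of 45, 50 and 55 bpm and the baseline QTcF values are illustrative assumptions. Appendix 6 flags sinus bradycardia only below 40 bpm.

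**Formula.** QTcF = QT / (60/HR)^(1/3).

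**Gap 1.** QT of 500 ms corresponds to QTcF 450 ms at 60 × (450/500)^3 = 43.7 bpm. Above that rate, any QT of 500 ms or more already satisfies the 450 ms half of trigger (a), so only the 60 ms rise decides whether (a) is met. A series started by (b) alone can therefore end with QT between 500 ms and

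min(500, baseline + 60) × (60/HR)^(1/3).

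The range opens only when baseline exceeds (QTcF at QT 500) − 60.

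| HR (bpm) | QTcF at QT 500 | Opens above baseline | Top of QT range, baseline 420 | Baseline 430 | Baseline 440 or more |
|---|---|---|---|---|---|
| 55 | 485.7 | 425.7 | 494.1 (empty) | 504.4 | 514.7 |
| 50 | 470.5 | 410.5 | 510.1 | 520.7 | 531.3 |
| 45 | 454.3 | 394.3 | 528.3 | 539.3 | 550.3 |

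Example: baseline 420 ms, 50 bpm, QT 505 ms. QTcF = 505 / 1.2^(1/3) = 475.2 ms, a rise of 55.2 ms. Trigger (b) fires and (a) does not. Two unchanged repeats both have QTcF under 500 ms, so the series ends after about 2 hours with QT still 505 ms.

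**Does Appendix 6 catch it?** QTcF of 480 ms corresponds to QT 494.1 ms at 55 bpm, 510.1 ms at 50 bpm and 528.3 ms at 45 bpm. With the rise below 60 ms, the part of gap 1 that Appendix 6 does not flag is none at 55 bpm, QT 500 to 510 ms at 50 bpm, and QT 500 to 528 ms at 45 bpm. The example above falls in it.

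**Does the 4-hour QT criterion catch it?** Showing that QT stays at or above 500 ms for more than 4 hours needs an ECG after the repeats have stopped. Inpatient postdose time points in the Schedule of Activities are 12 ± 1, 24 ± 2, 48 ± 2, 72 ± 4, 120 ± 4 and 168 ± 4 hours. The smallest gap between any two is 22 − 13 = 9 hours. In the row "Supine 12-lead ECG (triplicate)" the 12-hour cell appears blank, so scheduled ECGs themselves are at least 46 − 26 = 20 hours apart. Either way, no scheduled ECG falls inside the 4 hours.

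**Gap 2.** A QTcF above 500 ms escapes (a) when it is below baseline + 60. The width is baseline + 60 − 500: 0 ms at baseline 440, 5 ms at 445 and 10 ms at 450. It escapes (b) when the rate exceeds 60 × (QTcF/500)^3: 60.4 bpm at QTcF 501, 61.8 at 505 and 63.6 at 509.9. Example: baseline 448 ms, QTcF 505 ms, 65 bpm. The rise is 57 ms and QT = 505 × (60/65)^(1/3) = 491.7 ms. Neither trigger is met, although Appendix 6 lists this QTcF as a possible SAE.

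**The case against.** The strongest reply is that (b) was meant as absolute QTcF. Where the protocol plainly means the raw interval it says uncorrected, as in exclusion criterion 12 and section 9.3.2.1. It uses absolute as the opposite of change from baseline, as in the section 9.3.2.1 table and Appendix 6. The stop rule, the progressive-lengthening criterion, the consult rule and the over-read all name QTcF. On that reading both gaps disappear and the defect is one loose word. The reading is possible, but 8.2.4 does not state it, and the same section names QT and QTcF as distinct outputs. Site staff following the text would act on QT.

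A second reply is that screening on raw QT and deciding on corrected QT is a coherent design, as in exclusion criterion 12. That is a fair defence of releasing on QTcF at slow rates. However, 8.2.4 does not say so for (b), and that design would still leave gap 2. The 450 ms comparison is only a screening limit. It shows that QT of 500 ms or more above 43.7 bpm is not purely a rate effect, and no more than that.

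A third reply is that other cover exists. The investigator may escalate sooner, a qualified person compares each ECG with baseline, and the inpatient stay can be prolonged. Appendix 6 supplies "notifications from the core ECG laboratory to the investigator and Pfizer study team" and says its list is not exhaustive. SAP 6.6.4 also lists any single postdose QTcF above 500 ms. All of this stands. It limits the consequence, but it does not make the mandatory rule work as written.

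**Conclusion.** The mismatch holds on the text. Followed exactly, 8.2.4 lets a series started by (b) alone end with QT still at 500 ms or more at rates below 60 bpm. For a baseline QTcF of 440 ms or more, the QT left unresolved can reach 514.7, 531.3 or 550.3 ms at 55, 50 or 45 bpm. The range is empty at or below baselines of about 426, 411 and 394 ms respectively. Gap 2 is at most 10 ms wide, and narrower if (b) is applied to each tracing rather than to the triplicate mean.

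These sizes rest on the illustrative heart rates and on Day 1 baselines staying within the 450 ms screening limit. The documents give no frequency for either gap, and both should be rare in about 18 healthy volunteers. Investigator discretion and the Appendix 6 alerts remain. This is a minor point that merits a wording change.

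**What to change.** In both the repeat and the continuous-monitoring paragraphs of 8.2.4:

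- Keep QT of 500 ms or more as a trigger and add QTcF of 500 ms or more as a further one.
- End repeats only when the interval that triggered them, QT or QTcF, is below its threshold on 2 successive ECGs.
- Name QT as well as QTcF in the 8-hour cardiology-consult rule.
- Apply the over-read provision to the interval that triggered.

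This works whichever interval (b) was meant to use. Do not simply replace QT with QTcF in (b): that would close the mismatch by removing the mandatory repeats for QT of 500 ms or more at slow rates.

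The cost is wording in one protocol section and a few extra single ECGs in rare cases. A participant with a persistently slow rate could stay in hourly repeats longer: until QTcF is below 470.5 ms at 50 bpm, 454.3 ms at 45 bpm or 436.8 ms at 40 bpm. The last of these is already inside the screening limit. Such a participant could reach continuous monitoring or the 8-hour consult. The over-read can end this early, which is why it should cover QT explicitly.

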#### **8.2.5. Clinical Safety Laboratory Assessments**

See [Appendix 2](#) for the list of clinical safety laboratory tests to be performed and the [SoA](#) for the timing and frequency. All protocol-required laboratory assessments, as defined in [Appendix 2](#), must be conducted in accordance with the laboratory manual and the [SoA](#). Unscheduled clinical laboratory measurements may be obtained at any time during the study to assess any perceived safety issues.

The investigator must review the laboratory report, document this review, and record any clinically relevant changes occurring during the study in the AE section of the CRF. Clinically significant abnormal laboratory findings are those which are not associated with the underlying disease, unless judged by the investigator to be more severe than expected for the participant's condition.

All laboratory tests with values considered clinically significantly abnormal during participation in the study or within the time frame before the final planned follow-up visit

PFIZER CONFIDENTIAL

after the last dose of study intervention should be repeated until the values return to normal or baseline or are no longer considered clinically significant by the investigator or medical monitor.

If such values do not return to normal/baseline within a period of time judged reasonable by the investigator, the etiology should be identified and the sponsor notified.

See [Appendix 5](#) for suggested actions and follow-up assessments in the event of potential drug-induced liver injury.

Participants may undergo random urine drug testing at the discretion of the investigator. Urine drug testing conducted prior to dosing must be negative for participants to receive study intervention.

#### **8.2.6. COVID-19 specific assessments**

Participants will be tested for SARS-COVID-19 infection prior to being admitted to the clinic for confinement or site visit in compliance with the requirements from local regulations or the investigator. Additional testing for COVID-19 (e.g. chest radiograph) may be required by local regulations or by the investigator.

### **8.3. Adverse Events, Serious Adverse Events, and Other Safety Reporting**

The definitions of an AE and an SAE can be found in [Appendix 3](#).

AEs may arise from symptoms or other complaints reported to the investigator by the participant (or, when appropriate, by a caregiver, surrogate, or the participant's legally authorized representative), or they may arise from clinical findings of the Investigator or other healthcare providers (clinical signs, test results, etc.).

The investigator and any qualified designees are responsible for detecting, documenting, and recording events that meet the definition of an AE or SAE and remain responsible to pursue and obtain adequate information both to determine the outcome and to assess whether the event meets the criteria for classification as an SAE or caused the participant to discontinue the study (see [Section 7.1](#)).

[figure not shown]
During the active collection period as described in Section 8.3.1, each participant will be questioned about the occurrence of AEs in a nonleading manner.

In addition, the investigator may be requested by Pfizer Safety to obtain specific follow-up information in an expedited fashion.

